## **6.3 Blinding**

Participants and site staff (except for site pharmacists) will be blinded as to participant treatment arm assignments. Study product assignments are accessible to those HVTN CRS pharmacists, DAIDS protocol pharmacists and contract monitors, and SDMC staff who are required to know this information in order to ensure proper trial conduct. Any discussion of study product assignment between pharmacy staff and any other HVTN CRS staff is prohibited. The HVTN SMB members also are unblinded to treatment assignment in order to conduct review of trial safety.

When a participant leaves the trial prior to study completion, the participant will be told he or she must wait until all participants are unblinded to learn his or her treatment assignment.

In some cases, the CRS, PSRT, or study sponsor may believe unblinding of the site PI and participant would be appropriate to facilitate the clinical management of an AE or SAE. The HVTN Unblinding MOP specifies procedures for emergency unblinding, and for early unblinding for medical reasons.

## **6.4 Statistical analyses**

This section describes the final study analyses, unblinded as to treatment arm assignment. All safety data from enrolled participants will be analyzed according to the initial randomization assignment regardless of how many vaccinations they received. In the rare instance that a participant receives the wrong treatment at a specific vaccination time, the Statistical Analysis Plan (SAP) will address how to analyze the participant's safety data. Analyses are modified intent-to-treat in that individuals who are randomized but not enrolled do not contribute data and hence are excluded. Because of blinding and the brief length of time between randomization and enrollment—typically no more than 4 working days—very few such individuals are expected. The primary and secondary analyses of immunogenicity data are per-protocol in that only individuals who receive the expected vaccinations within the expected visit window contribute data.

Analyses for primary endpoints will be performed using SAS and R. All other descriptive and inferential statistical analyses will be performed using SAS, StatXact, or R statistical software.

#### **6.4.1 Analysis variables**

The analysis variables consist of baseline participant characteristics, safety, and immunogenicity for primary- and secondary-objective analyses.

#### **6.4.2 Baseline comparability**

Treatment arms will be compared for baseline participant characteristics using descriptive statistics.

#### **6.4.3 Safety/tolerability analysis**

Since enrollment is concurrent with receiving the first vaccination, all participants will have received at least 1 vaccination and therefore will provide some safety data.

##### **6.4.3.1 Reactogenicity**

The number and percentage of participants experiencing each type of reactogenicity sign or symptom will be tabulated by severity and treatment arm and the percentages displayed graphically by arm. For a given sign or symptom, each participant's reactogenicity will be counted once under the maximum severity for all injection visits. In addition, to the individual types of events, the maximum severity of local pain or tenderness, induration or erythema, and of systemic symptoms will be calculated. Wilcoxon tests will be used to test for differences in severity between arms.

##### **6.4.3.2 AEs and SAEs**

AEs will be summarized using MedDRA System Organ Class and preferred terms. Tables will show by treatment arm the number and percentage of participants experiencing an AE within a System Organ Class or within preferred term category by severity or by relationship to study product. For the calculations in these tables, a participant with multiple AEs within a category will be counted once under the maximum severity or the strongest recorded causal relationship to study product. Formal statistical testing comparing arms is not planned since interpretation of differences must rely heavily upon clinical judgment.

A listing of SAEs reported to the DAIDS Regulatory Support Center (RSC) Safety Office will provide details of the events including severity, relationship to study product, time between onset and last vaccination, and number of vaccinations received.

##### **6.4.3.3 Reasons for vaccination discontinuation and early study termination**

The number and percentage of participants who discontinue vaccination and who terminate the study early will be tabulated by reason and treatment arm.

## 6.4.4 Immunogenicity analysis

### 6.4.4.1 General approach

For the statistical analysis of immunogenicity endpoints analyses will be limited to participants who received all scheduled injections per protocol. Assay results that are unreliable, from specimens collected outside of the visit window, or from HIV-infected participants postinfection are excluded. Since the exact date of HIV infection is unknown, any assay data from blood draws 4 weeks prior to an infected participant's last seronegative sample and thereafter may be excluded. If an HIV-infected participant does not have a seronegative sample postenrollment, then all data from that participant may be excluded from the analysis.

Discrete categorical assay endpoints (eg, response rates) will be analyzed by tabulating the frequency of positive response for each assay by antigen and treatment arm at each timepoint for which an assessment is performed. Crude response rates and difference between treatment arms will be presented with their corresponding 95% CI estimates calculated using the score test method (50).

For quantitative assay data, graphical and tabular summaries of the distributions by antigen, treatment arm, and timepoint will be made. For all primary and secondary immunogenicity endpoints, box plots and plots of estimated reverse cumulative distribution curves will be used for graphical display of all of the study arms.

Mean or median (if normality assumption severely violated) assay readouts will be compared between arms and bootstrap CIs will be estimated.

More sophisticated analyses employing repeated measures methodology (for example, linear mixed models or marginal mean models fit by generalized estimating equations) may be utilized to incorporate immune responses over several timepoints and to test for differences over time.

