#### **4.5.2 Schedule**

Vaccinations will occur at months 0, 2, and 6. These immunization intervals were chosen based on prior studies with different Env proteins and are likely to lead to high peak antibody titers and high humoral response rates after the third vaccination. In previous trials with adjuvanted protein vaccines, peak immunogenicity has been observed after 3 doses of the protein, while a prolonged rest period between the 2nd and 3rd vaccinations is thought to enhance antibody maturation.

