### 5.2 Secondary objectives and endpoints

*Secondary objective 1:*

To evaluate and compare the breadth and kinetics of binding antibody responses elicited by the CH505TF gp120 proteins produced via transient and stable transfection methods

*Secondary endpoint 1:*

HIV-specific total IgG binding antibody responses against the homologous proteins and magnitude-breadth (M-B) measures against panels of cross-clade Env proteins and of cross-clade V2 proteins, as assessed by BAMA at peak timepoints (2 weeks after the 2nd and 3rd vaccinations) and late timepoints (3 and 6 months after the 3rd vaccination)

*Secondary objective 2:*

To evaluate and compare the IgG subclass and IgA binding antibody responses elicited by the CH505TF gp120 proteins produced via transient and stable transfection methods

*Secondary endpoint 2:*

HIV-specific IgG subclass and IgA binding antibody response rates and magnitudes against homologous Env and V2 proteins, as assessed by BAMA at 2 weeks after the 2nd vaccination, 2 weeks after the 3rd vaccinations, and 3 and 6 months after the 3rd vaccination

*Secondary objective 3:*

To evaluate the ability of the two CH505TF gp120 proteins to elicit HIV-specific neutralizing antibodies (nAbs)

*Secondary endpoint 3:*

Magnitude and breadth of nAb responses against a panel of viral isolates as assessed by area under the M-B curves 2 weeks after the 2nd and 3rd vaccinations

*Secondary objective 4:*

To evaluate the avidity of antibody responses elicited by the CH505TF gp120 proteins

*Secondary endpoint 4*

Avidity of Env-specific IgG antibodies at baseline and 2 weeks after the 3rd vaccination

*Secondary objective 5:*

To evaluate HIV-specific T-cell responses induced by the two CH505TF gp120 proteins

*Secondary endpoint 5:*

Response rate, magnitude, and polyfunctionality of CD4+ T-cell responses as assessed by intracellular cytokine staining (ICS) assays 2 weeks after the 2nd and 3rd vaccinations

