### **7.3.3 Discontinuing vaccination for a participant**

Under certain circumstances, an individual participant's vaccinations will be permanently discontinued. Specific events that will result in stopping a participant's vaccination schedule include:

- Co-enrollment in a study with an investigational research agent (rare exceptions allowing for the continuation of vaccinations may be granted with the unanimous consent of the HVTN 123 PSRT)
- Clinically significant condition (ie, a condition that affects the immune system or for which continued vaccinations and/or blood draws may pose additional risk), including but not limited to the following:
  - Pregnancy (regardless of outcome)
  - HIV infection
  - Any grade 4 local or systemic reactogenicity symptom, lab abnormality, or AE that is subsequently considered to be related to vaccination
  - Any grade 3 lab abnormality that is subsequently considered to be related to vaccination
  - Other grade 3 clinical AE that is subsequently considered to be related to vaccination with the exception of fever, vomiting, and subjective local and systemic symptoms. For grade 3 injection site erythema and/or induration, upon review, the PSRT may allow continuation of vaccination

- SAE that is subsequently considered to be related to vaccination
- Clinically significant type 1 hypersensitivity reaction associated with study vaccination. Consultation with the HVTN 123 PSRT is required prior to subsequent vaccinations following any type 1 hypersensitivity reaction associated with study vaccination
- Investigator determination in consultation with Protocol Team leadership (eg, for repeated nonadherence to study staff instructions)

Participants discontinuing study product for reasons other than HIV infection should be counseled on the importance of continuing with the study and strongly encouraged to participate in follow-up visits and protocol-related procedures per the protocol for the remainder of the trial, unless medically contraindicated (See HVTN 123 SSP).

Participants diagnosed with HIV infection during the study should be encouraged to participate in follow-up visits as indicated in Section [9.13](#)

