### 10.3 Immunogenicity timepoints

The immunogenicity timepoints in this study occur: 2 weeks after the 2nd vaccination visit, 2 weeks after the 3rd vaccination visit, 3 months after the 3rd vaccination visit, and 6 months after the 3rd vaccination visit. Endpoint assays for humoral and cellular responses are performed on samples collected from participants at the immunogenicity timepoints and may be performed on samples collected at baseline. Depending on the initial results, assays for humoral and cellular responses may be performed on samples collected from participants at other timepoints; the schedule is shown in [Appendix E](#).

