## **4 COHORT DEFINITION**

Analyses are modified intent-to-treat in that individuals who are randomized but not enrolled do not contribute data and hence are excluded. Because of blinding and the brief length of time between randomization and enrollment - typically no more than 4 working days - very few such individuals are expected. The primary and secondary analyses of immunogenicity data are per-protocol in that only individuals who receive the expected vaccinations within the expected visit window contribute data.

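### Requiring all three injections for every immunogenicity analysis drops valid post-dose-2 samples from anyone who later misses dose 3; the per-protocol set should be defined visit by visit

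*Protocol*

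**What the plan says.** **Who is analysed.** Protocol section 6.4.4.1 says that for immunogenicity endpoints "analyses will be limited to participants who received all scheduled injections per protocol", and SAP section 9 repeats the sentence. Neither place varies the rule by visit. Protocol section 6.4 is looser: "only individuals who receive the expected vaccinations within the expected visit window contribute data". SAP section 4 uses the same wording, introduced by "The primary and secondary analyses of immunogenicity data are per-protocol". The modified intent-to-treat language in both documents removes only people who were randomized but never enrolled.

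**When injections and samples fall.** Protocol section 4.5.2: "Vaccinations will occur at months 0, 2, and 6". Protocol section 10.3 lists the first immunogenicity timepoints as "2 weeks after the 2nd vaccination visit, 2 weeks after the 3rd vaccination visit". Appendices E and F place these samples on day 70 (M2.5) and day 182 (M6.5), with dose 3 on day 168. Secondary endpoint 3 is the "area under the M-B curves 2 weeks after the 2nd and 3rd vaccinations". Secondary endpoints 1, 2 and 5 also include the visit 2 weeks after dose 2.

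**Why dose 3 may be missed.** Under section 7.3.2 a dose whose window has passed is not given, and the participant is asked to stay in follow-up. Section 7.3.3 lists reasons for stopping permanently, among them "Any grade 3 lab abnormality that is subsequently considered to be related to vaccination", along with other related events, pregnancy and HIV infection.

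**The concern.** A participant who had doses 1 and 2 in window and gave a good sample on day 70 has met every condition that bears on that sample. Under the literal rule the result is still discarded if dose 3 is missed months later. Two things follow.

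- Precision is lost at M2.5 in arms of only 15.
- The randomized comparison at M2.5 becomes conditional on an event after the measurement. Some stopping reasons are product-related, and the trial exists partly to learn whether the two products differ in safety, so this selection need not be equal between arms.

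The same logic reaches M0. SAP section 9.3.1 compares T1 with T2 on samples drawn before any injection, yet inclusion would depend on receiving all three.

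Because Protocol section 6.4 and SAP section 4 can be read as requiring only the injections due by the time of the sample, two analysts could arrive at different M2.5 denominators.

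**Working it through.** **1. Timing.** Dose 3 is due on day 168 and the post-dose-2 sample on day 70: 168 − 70 = 98 days. The exclusion is decided about 14 weeks after the measurement.

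**2. Does any other text restore the data?** No section defines the set by timepoint, keeps data collected before a missed dose, or plans a wider sensitivity set for immunogenicity. The optional repeated-measures models appear under the same restriction in Protocol section 6.4.4.1 and SAP section 9. Where SAP section 9.3.1 says all participants, it means responders and non-responders together, within the restricted set.

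**3. The plan's own figure.** Protocol Table 6-3 gives power 0.74 for n = 15 per arm, SD 1.4 of log_e(FI) and margin 1/4, two-sided alpha 0.05. The true ratio is not stated; I assume 1.

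- Standard error = 1.4 × √(2/15) = 0.511
- Noncentrality = log_e(4)/0.511 = 1.386/0.511 = 2.71, with 28 degrees of freedom
- Power by noncentral t = 0.745, in agreement with the table

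This figure is for non-inferiority of the binding response, whose primary endpoint is at M6.5. Someone without dose 3 is excluded at M6.5 under the current rule and under a visit-specific one, so it does not change.

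**4. Precision at M2.5.** The documents give no missed-dose rate, so the losses below are assumptions. The 95% CI half-width for a difference in means, in SD units, is t(0.975, 2n − 2) × √(2/n).

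| Lost per arm | n per arm | Half-width (SD units) | Relative to n = 15 |
|---|---|---|---|
| 0 | 15 | 2.048 × 0.365 = 0.748 | 1.00 |
| 1 | 14 | 2.056 × 0.378 = 0.777 | 1.04 |
| 2 | 13 | 2.064 × 0.392 = 0.809 | 1.08 |
| 3 | 12 | 2.074 × 0.408 = 0.847 | 1.13 |

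Working in SD units avoids borrowing the SD of 1.4, which the protocol takes from HVTN 505 and does not give for M2.5.

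**5. How likely is it to arise?** If each of 30 participants missed dose 3 independently with probability p, the chance of at least one is 1 − (1 − p)^30: 0.79 for p = 5% and 0.96 for p = 10%. The expected numbers are 30 × 0.05 = 1.5 and 30 × 0.10 = 3. Both rates are assumptions.

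**6. Bias.** Its size depends on how stopping differs by arm and how strongly stopping relates to the M2.5 response. The documents give neither. If stopping is unrelated to response, the bias is zero. Any figure would be hypothetical, so I give none.

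**The case against.** **One fixed cohort is a legitimate choice.** Per-protocol analysis is declared openly. Secondary objective 1 concerns kinetics, and following the same people from M2.5 to M12 keeps visits comparable. This stands as a reason to display completers of all three doses. It is not a reason to make them the only set for the M2.5 arm comparison.

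**Forced stopping may be uncommon.** Section 7.3.3 exempts grade 3 fever, vomiting and subjective symptoms, and the PSRT may allow continuation after grade 3 erythema or induration. Section 4.9.1 reports one grade 3 local reaction in HVTN 115 Part A (42 enrolled), with all other reactogenicity mild to moderate. Those data are interim and cover only the Stable product. Section 6.4.3.3 tabulates discontinuations by reason and arm, so unequal loss would be visible. This limits the likely size. It does not mend the rule.

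**Conditioning remains later.** A visit-specific per-protocol set still conditions on dose 3 at M6.5, M9 and M12. True: the change removes only conditioning on events after the sample.

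Three stronger readings are tempting and are not supported:

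- *Primary power falls.* A reader might enter 13 or 12 per arm in the non-inferiority calculation and report 0.68 or 0.64 in place of 0.745. No 1/4-margin test is planned at M2.5, and the M6.5 set is the same under either rule.
- *A specified M2.5 table will be wrong.* SAP sections 9.3 and 9.3.1 cover BAMA only at M0 and M6.5, section 9.2 names no M2.5 visit for neutralization, and section 9.1 (ICS) is still template text.
- *The sections flatly contradict each other.* The looser wording can be read to agree with the strict rule. It is ambiguous.

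**Conclusion.** The point holds as a defect in the definition of the analysis set for the M2.5 secondary endpoints. Read literally, Protocol section 6.4.4.1 and SAP section 9 discard valid post-dose-2 samples because of a later event that may be product-related, and nothing else in either document restores them. The rule also reaches the M0 comparison in SAP section 9.3.1.

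The size is modest. Under the assumed loss of 1 to 3 of 15 per arm, the M2.5 interval is about 4% to 13% wider; the documents cannot say whether such losses will occur or whether they would bias the comparison. The primary endpoint and its stated power are untouched.

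The point matters in practice because both documents still list the M2.5 endpoints, Appendix E (footnote 6) schedules immunogenicity assays at M2.5, and SAP section 9.2.1 plans neutralization comparisons by visit. It should be corrected because the correction is cheap.

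**What to change.** In Protocol sections 6.4 and 6.4.4.1 and SAP sections 4 and 9, use one definition: the per-protocol set for a visit is the participants who received, in window, all injections scheduled before that sample.

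- M0: no injection required
- M2.5: doses 1 and 2
- M6.5, M9 and M12: doses 1 to 3

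Leave the other exclusions (unreliable results, samples out of window, post-infection samples) as they are. For kinetics displays, also show the participants who received all three doses. Settle the wording before any M2.5 results by arm are seen.

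The cost is a few sentences, but in both documents, so it includes a protocol wording change. Denominators will differ slightly between visits and should be printed in each table. No new samples or assays are needed, and the M6.5 primary analysis is unchanged.

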### 6.4.4.2 Multivariate display of immunogenicity endpoints

Data visualization techniques may be used to explore the relationship among immunogenicity readouts. The set of readouts may be based on the set of primary endpoints, or on immunogenicity endpoints that also include secondary or exploratory endpoints. To understand the relationship between pairs of readouts, scatter plots may be used when the number of readouts is small or for a larger number of readouts, a heatmap showing the degree of correlation between any two pairs. Principal component analysis (PCA) and associated 'biplots' of the scores and loadings are particularly useful to understand associations between readouts, especially when readouts are correlated (51). PCA is a method to reduce the dimensionality of the number of readouts to a smaller set of values (principal components) that are normalized linear combinations of the readouts in such a way that the first principal component accounts for the most variability in the data and subsequent components, while maximizing variability, are uncorrelated with

each other. A ‘biplot’ displays the first and second principal component scores and principal component loadings. The x-axis is the value from the first principal component and the y-axis is the second principal component, where each axis label includes the percentage of variation in the total set of readouts captured by the principal component. The top axis is the first principal component loadings and the right axis is the second principal component loadings. An arrow is drawn for each immunogenicity readout (eg, Env-specific CD4+ T cell polyfunctionality score, Env-specific CD8+ T cell total magnitude) from the origin to the point defined by its first two principal component loadings. The length of the arrow represents the amount of total variation of the set of readouts captured by the given readout. The direction of an arrow conveys the extent to which the variation of a readout is in the direction of the first or second principal component. The angle between two arrows conveys information about the correlation of the two readouts, with a zero degree angle denoting perfect correlation and a 90 degree angle denoting no correlation. Each arrow on the biplot is labeled by the immunogenicity readout it represents. A biplot is annotated with key meta-information such as the treatment arm (most common application) or a demographic category. Depending on the application, K-means clustering and hierarchical clustering may also be applied for multivariate graphical display of immunogenicity readouts.

#### 6.4.4.3 Analysis of multiplexed immunoassay data

Two approaches will be considered to evaluate the magnitude and breadth of these responses. First, M-B curves maybe employed to display individual- and group-level response breadth as a function of magnitude. Two choices are to compare the M-B curves among vaccine arms, as follows: a non-parametric Wilcoxon rank sum test on the subject-specific area-under-the M-B curve (AUC-MB) or a Kolmogorov-Smirnov type test on the 2 group-average M-B curves. Simulations can be used to obtain 2-sided p-values for the latter test. Second, a weighted-average score-like variable may be constructed to account for the correlations between analytes as an integrate magnitude of responses to multiple analytes. Similar group comparison methods described in the first approach may be adopted. Details of either approach will be described in the SAP.

